### 2.1.3 *Inferential statistics*

All statistical comparisons will be made using two-sided tests at the 0.05 significance level unless specifically stated otherwise.

The change from baseline in  $PPR_2$  and  $PPR_4$  at Day 8 will be analysed using an analysis of covariance (ANCOVA) model, including treatment, subject and period as fixed effects, and  $PPR_2$  (or  $PPR_4$ ) at baseline (i.e., Day -1) as a covariate. The adjusted mean change from baseline obtained with each treatment and the adjusted mean difference between HFA-152a and HFA-134a with their 95% confidence intervals (CIs) and p-values will be estimated by the model.

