The selected treatment dose (i.e. 5 inhalations BID) corresponds to the maximum total daily dose of HFA-134a propellant allowed for administration with the Clenil pMDI device, according to the current summary of product characteristics (SmPC) (for Clenil 100 µg, the maximum allowed daily dose is 1000 µg, administered as 500 µg BID).

The effect on MCC of each propellant will be evaluated by the change, from baseline (before administration of each propellant) to the end of the 8-day treatment period, in the percent particle retention (PPR) evaluated at 0 (immediately), 2 and 4 hours after the administration of a radiotracer.

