12.3.3 STUDY VARIABLES

MCC variables (in whole lung) evaluating the primary objective of the study (see [Section 8](#)) will be analysed in the ITT and PP sets, as follow:

- The change from baseline in PPR₂ at Day 8 will be analysed using an analysis of covariance (ANCOVA) model, including treatment, subject and period as fixed effects, and PPR₂ at Day -1 as a covariate. The adjusted mean change from baseline obtained with each treatment and the adjusted mean difference between HFA-152a and HFA-134a with their 95% confidence intervals (CIs) and p-values will be estimated by the model;
- The change from baseline in PPR₄ at Day 8 will be analysed using the same model used for the change from baseline in PPR₂.

The MCC variable completing the evaluation of the primary objective will be analysed as follow:

- The change from baseline in AUC₀₋₄ after the inhalation of radiolabelled particles will be summarised using descriptive statistics.

Descriptive statistics will also be provided for the MCC data (in whole lung) collected at all other post-dose timepoints (see [Section 7.2.1](#)).

Figures will be provided for the mean change from baseline in PPR (in whole lung), by treatment arm and each post-dose timepoints.

Data of other MCC parameters (i.e. MCC on central region and on peripheral region, and central/peripheral ratio, see [Section 7.2.1](#)) will be listed only.

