### 2.1.4 *Presentation of results*

All MCC variables in right whole lung (PPR in right whole lung region (%), PPR in right central lung region (%), PPR in right peripheral lung region (%) and Right Central/Peripheral Ratio) (including  $AUC_{0-4}$  only for right whole lung region) will be summarised by means of descriptive statistics by treatment. Actual values (with their 95% CI) and changes from baseline (with their 95% CI) will be tabulated separately.

The ANCOVA model will be performed for change from baseline of  $PPR_2$  and  $PPR_4$  at Day 8. The results will be tabulated, including the estimates (mean, 95% CI, p-value) of the model estimated changes from baseline and difference between HFA-152a and HFA-134a in change from baseline.

Graphs of the mean actual values and the mean changes from baseline over time will be prepared for PPR (in right whole lung region, right central lung region and right peripheral lung region) by treatment.

All MCC data will be listed. All MCC data for the whole and the left lung will be listed only.

	Statistical Analysis Plan	
CLI-05993AB6-06	Final Analysis	Final 1.0 of 05OCT2023

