## **5.4 PRESENTATION OF RESULTS**

### **5.4.1 Calculation of descriptive statistics and percentages**

For continuous parameters, full descriptive statistics will only be presented if there are at least 2 non-missing observations. Alternatively, only the number of non-missing data points and mean are shown.

Descriptive statistics will include the number of non-missing data points, the arithmetic mean, the standard deviation (SD), the median, minimum and maximum.

Descriptive statistics will additionally include 95% (or 90%) confidence interval (CI) on the mean (based on t-distribution, without continuity correction).

Mean, median, SD and CI will be presented with one more decimal place than the individual values, with a maximum of 4 decimal places. Minimum and maximum will be presented with the same number of decimal places as the individual values, with a maximum of 3 decimal places.

For graphs showing mean values, a 95% CI flag will be shown (based on t-distribution, without continuity correction).

For event-type data, the denominator will be all subjects in the analysis set and phase and period. All treatments will be shown, even if no events are present.

For tabulations by planned treatment, subjects who discontinued the study early will not be included in the denominator of the treatment periods they did not attend.

P-values will be presented with three decimal places (Note: Any p-value less than 0.001 will be presented as <0.001 and any p-value greater than 0.999 will be presented as >0.999), ratios with three decimal places and test statistics with two decimal places.

For frequency tabulations, missing values will not be included in the denominator count when computing percentages.

Percentages will be shown with one decimal place.

	Statistical Analysis Plan	
CLI-05993AB6-06	Final Analysis	Final 1.0 of 05OCT2023

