Number	Title	Analysis Set	TLFs Library Template Number
STUDY VARIABLES			
14.2.1.1.1	MCC Variables: Summary of Actual Values (ITT Analysis Set) Descriptive statistics of study variables (right whole lung: PPR and AUC 0-4 ) results per parameter and analysis visit and time point window. Table sorted by analysis window. Each parameter will begin on a new page.	ITT	TPT002
14.2.1.1.2	MCC Variables: Summary of Actual Values (PP Analysis Set) Descriptive statistics of study variables (right whole lung: PPR and AUC 0-4 ) results per parameter and analysis visit and time point window. Table sorted by analysis window. Each parameter will begin on a new page.	PP	TPT002
14.2.1.2.1	MCC Variables: Summary of Changes from Baseline (ITT Analysis Set) Descriptive statistics of changes from baseline in study variables (right whole lung: PPR and AUC 0-4 ) results per parameter and analysis window. Table sorted by analysis window. Each parameter will begin on a new page.	ITT	TPT003
14.2.1.2.2	MCC Variables: Summary of Changes from Baseline (PP Analysis Set) Descriptive statistics of changes from baseline in study variables (right whole lung: PPR and AUC 0-4 ) results per parameter and analysis window. Table sorted by analysis window. Each parameter will begin on a new page.	PP	TPT003
14.2.1.3.1	MCC Variables: Statistical Analysis of Changes from Baseline in PPR2 in Right Whole Lung Region (ITT Analysis Set) Results from the ANCOVA model on change from baseline at Day 8 for PPR 2 as described in section 2.1.3	ITT	ANT001
14.2.1.3.2	MCC Variables: Statistical Analysis of Changes from Baseline in PPR2 in Right Whole Lung Region (PP Analysis Set) Results from the ANCOVA model on change from baseline at Day 8 for PPR 2 as described in section 2.1.3	PP	ANT001
14.2.1.4.1	MCC Variables: Statistical Analysis of Changes from Baseline in PPR4 in Right Whole Lung Region (ITT Analysis Set) Results from the ANCOVA model on change from baseline at Day 8 for PPR 4 as described in section 2.1.3	ITT	ANT001
14.2.1.4.2	MCC Variables: Statistical Analysis of Changes from Baseline in PPR4 in Right Whole Lung Region (PP Analysis Set) Results from the ANCOVA model on change from baseline at Day 8 for PPR 4 as described in section 2.1.3	PP	ANT001
SAFETY			
ADVERSE EVENTS			

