## 9. APPENDICES

### 9.1 SAS CODE

The SAS code in this section is an example and might differ from the actual code used in the statistical analysis.

ANCOVA

```
proc mixed data=model;
  class usubjid treatment period;
  model chg = base treatment period usubjid;
  lsmeans treatment / cl alpha=0.05 diff;
  ods output lsmeans=lsmeans diffs=diffs;
run;
```

	Statistical Analysis Plan	
CLI-05993AB6-06	Final Analysis	Final 1.0 of 05OCT2023

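### The fixed-subject ANCOVA does not assure the 5% level for each propellant's own change from baseline; the t-based CI already planned should carry that conclusion

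*SAP*

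**What the plan says.** Protocol 12.3.3 specifies an ANCOVA of the Day 8 change in PPR2 and PPR4 "including treatment, subject and period as fixed effects", with the matched Day -1 value as covariate. SAP 2.1.3 repeats it and reports from it "The adjusted mean change from baseline obtained with each treatment and the adjusted mean difference between HFA-152a and HFA-134a with their 95% confidence intervals" and p-values, under a two-sided 0.05 level for all comparisons. The example code in SAP 9.1 agrees: "model chg = base treatment period usubjid", with no RANDOM or REPEATED statement, followed by LS means with confidence limits. SAP 2.1.4 tabulates the model results, "including the estimates (mean, 95% CI, p-value) of the model estimated changes from baseline".

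The same section plans a second interval for the same quantity: "changes from baseline (with their 95% CI) will be tabulated separately". SAP 5.4.1 gives its basis: "Descriptive statistics will additionally include 95% (or 90%) confidence interval (CI) on the mean (based on t-distribution, without continuity correction". It appears in the table titled "MCC Variables: Summary of Changes from Baseline (ITT Analysis Set") and its PP counterpart. The SAP does not say which interval carries the conclusion on a single propellant.

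**The concern.** Protocol 1.2 gives the within-propellant change a role of its own: "The effect on MCC of each propellant will be evaluated by the change, from baseline". A reader may therefore take the per-propellant p-value as the answer for that propellant.

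Subject effects cancel in the HFA-152a minus HFA-134a contrast, so a fixed-subject model gives it the right standard error. They do not cancel in a single LS mean. That standard error treats the mean Day -1 value as known, cannot see a Day 8 shift that a subject shows under both propellants, and assigns both propellants the same pooled variance. The test can then reject too often for one propellant and too rarely for the other, and a statement that a propellant did or did not change clearance would not carry its stated error rate.

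**Working it through.** **Inputs from the documents.** 20 subjects randomised, at least 18 evaluable (SAP 1.3); two-sided 0.05 (SAP 2.1.3); the model of SAP 2.1.3 and 9.1. Residual df with complete pairs are n - 3 = 15 or 17.

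**Assumptions, because the documents give no PPR variances.** Between-subject SD 10 points; within-subject variance w = 5² = 25; r = share of w common to Day -1 and Day 8 of the same period, with L = 1 - r; no mean effect; any subject-specific Day 8 shift has SD τ.

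**Step 1, residual variance.** A subject's change has variance 2Lw. Its within-subject slope on the Day -1 value is -L. The residual variance is therefore σ² = 2Lw - L²w = Lw(2 - L).

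**Step 2, variance the model reports for one LS mean.** σ²/(2n) for the overall mean plus σ²/(2n) for half the treatment difference gives σ²/n = Lw(2 - L)/n. The small term for estimating the slope is ignored.

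**Step 3, actual variance with no shift.** LS means are taken at the overall mean baseline, so the overall part is the unadjusted mean change, with variance 2Lw/(2n) = Lw/n. Adding σ²/(2n) gives Lw(2 - L/2)/n.

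**Step 4, ratio of actual to reported SE.** k = √[(2 - L/2)/(2 - L)] = 1.22, 1.08, 1.03, 1.01 at r = 0, 0.5, 0.8, 0.95. Simulation gave 1.21-1.23, 1.07-1.08, 1.02-1.03, 1.00-1.02.

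**Step 5, shifts** (additions to n × variance).
- Common to both propellants: actual + τ², reported + 0.
- HFA-152a only: actual + τ² for HFA-152a and + 0 for HFA-134a; reported + τ²/2 for both.
- Independent, equal variance: actual + τ², reported + τ².

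**Step 6, level.** P(|t| > c/k) on n - 3 df. For n = 18, r = 0, no shift: actual 37.5, reported 25, k = √1.5 = 1.22, c = 2.131, level 10.2%. For a common shift SD 2.5 at r = 0.95: (2.47 + 6.25)/2.44 = 3.58, k = 1.89, level 28%.

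Formula for n = 18 (whole per cent), with the simulated range for n = 18 and 20 in brackets (10,000 runs per cell):

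| Setting | r = 0 | r = 0.5 | r = 0.8 | r = 0.95 |
|---|---|---|---|---|
| No shift | 10 (9.5-10.4) | 7 (6.2-6.9) | 6 (5.2-5.8) | 5 (4.8-5.4) |
| Common shift, SD 2.5 | 13 (12.0-12.7) | 10 (9.9-10.8) | 13 (12.5-13.8) | 28 (26.5-27.4) |
| Independent shifts, SD 2.5 or 5 | 8-9 (7.2-9.2) | 6 (5.5-6.4) | 5 (5.0-5.5) | 5 (4.5-5.4) |
| HFA-152a-only shift, SD 5: HFA-152a | 12 (11.6-12.1) | 10 (9.9-10.2) | 11 (11.1-11.2) | 14 (13.2-13.9) |
| HFA-152a-only shift, SD 5: HFA-134a | 5 (4.7-4.8) | 2 (2.4-2.5) | 1 (0.5-0.7) | below 0.1 (below 0.1) |

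Other simulated results:
- An HFA-152a-only shift of SD 2.5 gave 7.9-11.1% for HFA-152a and 0.6-8.8% for HFA-134a. A common shift of SD 5 gave about 20% to 51%.
- Over the complete-pairs grid (two sample sizes, seven shift settings, four values of r) the between-propellant contrast stayed at 4.5-5.4% and the one-sample t on each propellant's changes at 4.5-5.6%.
- If 2 of 20 subjects lose one period, with no shift, the planned levels are 10.2-11.4%, 6.3-7.0%, 5.3-5.8% and 4.9-5.5%.
- At n = 18 and r = 0, raising the common shift SD from 0 to 5 leaves the mean model CI width unchanged (5.03 and 5.02), while the t-based width goes from 6.93 to 8.49. The model interval does not register that subjects differ in their response.

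**The case against.** **A fixed subject effect declares inference about these volunteers only.** Read as conditional on the enrolled subjects and their observed Day -1 values, the planned CI misses 4.6-5.8% of the time, which is about nominal. This stands for the CI, but the SAP never states that reading. Nor does it rescue the p-value: given the observed Day -1 values, the expected change is not zero even when the propellant does nothing, so testing against zero is not a test of no change.

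**The hierarchy is readable.** The ANCOVA sits under inferential statistics and the t-based CI under descriptive statistics. That is fair, but it only makes the interval with the unassured level the operative one.

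**A random-subject ANCOVA would keep the baseline and period adjustment.** With no shift or a common shift and complete pairs, its simulated level was 3.3-5.7%. It still pools the two propellants, however: under an HFA-152a-only shift it gave 6-14% for HFA-152a and 0-3% for HFA-134a. It does not displace the t.

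**The variances are assumed.** True. Without a shift, r of 0.5 or more gives only 4.8-6.9%, and the 27% figure needs both r = 0.95 and a shift that the documents do not show to exist.

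**A one-sample p-value is new, and with no untreated arm no per-propellant p-value isolates a propellant effect.** This stands. Spirometry and ECGs precede the Day 8 scan (Protocol Table 3) and are not scheduled on Day -1 (Protocol Table 2). It is a reason to label or drop these p-values, not to keep the planned ones unqualified.

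**Conclusion.** The concern holds and is minor. The 5% level is not assured for either propellant's own change, and the error can go either way. With no shift the excess depends on r, from about 10% at r = 0 to about 5% at r = 0.95. Shifts can raise it further or, for the propellant without them, push the level well below 5%. All of these levels rest on the assumed SDs, r and shift settings; the direction of the argument does not. The HFA-152a minus HFA-134a comparison is unaffected, the study is described as exploratory with no formal sample size, no decision rule uses the per-propellant p-values, and a t-based interval is already planned.

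**What to change.** 1. Keep the fixed-subject ANCOVA for the HFA-152a minus HFA-134a difference only.
2. Take each propellant's mean change and 95% CI from the one-sample t on subject-level changes, already the CI basis of Tables 14.2.1.2.1 and 14.2.1.2.2. If a p-value is wanted, use the matching one-sample t-test.
3. Remove the LS-mean CIs and p-values from the 14.2.1.3 and 14.2.1.4 tables, or label them as conditional on the enrolled subjects and observed baselines and not for inference on each propellant.
4. Record the choice in SAP 6.1, because Protocol 12.3.3 prespecifies these outputs.
5. Footnote two limits: the unadjusted means need not subtract to the ANCOVA difference, and without an untreated arm a change from baseline also contains visit and procedure effects.

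The work is an edit to SAP 2.1.3 and 2.1.4, an entry in 6.1, two footnotes and a few lines of SAS; the label option is a footnote only.

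The statistical price, under the same assumptions:
- With no shift, the t-based CI is 38-39% wider than the planned one at r = 0, 12-13% at r = 0.5 and 3% at r = 0.8, and 1% narrower at r = 0.95. Part of this is the lost baseline adjustment.
- The t does not adjust for period. An assumed 3-point period effect makes it conservative, at 0.8-5.0%.
- The difference between the two t-based means departs from the ANCOVA difference by 1.3-1.4 points on average at r = 0, 0.6-0.7 at r = 0.5 and 0.3-0.4 at r = 0.8.

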### 2.1.4 *Presentation of results*

All MCC variables in right whole lung (PPR in right whole lung region (%), PPR in right central lung region (%), PPR in right peripheral lung region (%) and Right Central/Peripheral Ratio) (including  $AUC_{0-4}$  only for right whole lung region) will be summarised by means of descriptive statistics by treatment. Actual values (with their 95% CI) and changes from baseline (with their 95% CI) will be tabulated separately.

The ANCOVA model will be performed for change from baseline of  $PPR_2$  and  $PPR_4$  at Day 8. The results will be tabulated, including the estimates (mean, 95% CI, p-value) of the model estimated changes from baseline and difference between HFA-152a and HFA-134a in change from baseline.

Graphs of the mean actual values and the mean changes from baseline over time will be prepared for PPR (in right whole lung region, right central lung region and right peripheral lung region) by treatment.

All MCC data will be listed. All MCC data for the whole and the left lung will be listed only.

	Statistical Analysis Plan	
CLI-05993AB6-06	Final Analysis	Final 1.0 of 05OCT2023

### 3. SAFETY ANALYSES

#### 3.1 ADVERSE EVENTS

##### 3.1.1 *Available data*

Adverse events (AEs) are coded into system organ classes and preferred terms using the medical dictionary for regulatory activities (MedDRA, see section 9.3). For each AE, start and stop date(time)s are collected as well as intensity, a seriousness flag, seriousness criteria, treatment-relationship, action taken towards the study treatment and outcome.

##### 3.1.2 *Derivation rules*

Pre-treatment AEs are defined as AEs starting between date of informed consent with 00:00 added as time part and the date(time) of first study treatment administration – 1 minute, extremes included.

Treatment-emergent adverse events (TEAE) are defined as AEs starting on or after first administration of any study treatment.

Adverse drug reactions (ADRs) are defined as TEAEs related to study treatment or with missing relationship.

Based on their start date(time), AEs will be allocated to the phase and period during which they started. Phases and periods are defined in section 5.2.1. In case the AE start date(time) is incomplete or missing and the AE could consequently be allocated to more than one phase or period, a worst-case allocation will be done as detailed below:

- Treatment phase vs. non-treatment phase: AE will be allocated to the treatment phase.
- Multiple treatment periods: AE will be allocated to all treatment periods, except periods for which the available parts of the AE start or stop date(time) provides evidence the AE did not occur during that period.

A fatal AE is defined as an AE with outcome ‘fatal’.

An AE for which the study treatment was discontinued is defined as an AE with action taken ‘drug permanently withdrawn’.

	Statistical Analysis Plan	
CLI-05993AB6-06	Final Analysis	Final 1.0 of 05OCT2023

AE onset and duration will be calculated as follows:

- AE onset day (vs. first administration) =
  - AE start date < date of first administration: AE start date – date of first administration
  - AE start date ≥ date of first administration: AE start date – date of first administration + 1 day
- AE onset day (vs. start of period) = AE start date – analysis period start date + 1 day
- AE duration (rounded as detailed in section 5.3.3) =
  - If start and stop date/time are available:
    - AE end date/time – AE start date/time + 1 minute

Note: If AE duration is less than 1 hour, the duration will be presented in minutes. If the AE duration is 1 hour or more, but less than 1 day, it will be presented in hours. If AE duration is 1 day or more, it will be presented in days.

- If only start and stop dates are available:
  - AE end date – AE start date + 1 day
  - date of last contact – AE start date + 1 day (when the AE start date is fully known but the AE is not resolved at the end of the study); in this case the duration will be presented as “>x days”.

